This study is a prospective, randomized controlled trial that will study the postoperative clinical outcomes of levothyroxine supplementation in delayed recovery or prolonged ventilation patients post cardiac surgery.

Randomization will be performed using a computer-generated randomization sequence and allocation concealment to be maintained all through the time of procedure, by using opaque, numbered, and sealed envelopes.

The study protocol will receive ethical approval from the Research Ethical Committee/ Institutional Review Boards, Faculty of Medicine Ain Shams University.

Informed consent will be obtained from each patient before patients' allocation.

Type of the study: prospective randomized clinical trial study protocol.

Study Setting: The operating theaters and ICU of Cardiothoracic institute of Ain Shams University Hospitals.

Study period: one year.

Sample Size:

Using PASS 15 program for sample size calculation, setting power at 80% and alpha error at 0.05, it is estimated that sample size of 25 patients per group total 50 patients can detect an effect size .80 or the difference between two groups regarding different qualitative outcome measures using two-sized a z test

Study population:

Inclusion criteria:

- Age group: Adult patients from age of 45 to 70 years.

Hypothyroidism was reported to be strongly related to cardiovascular disease, respiratory complications, neurological complications, and a significant difference in ventilator weaning time [3].

- Sex: Both sexes
- Elective, urgent and emergency open heart surgeries.

Exclusion criteria:

- Patients refuse to give informed consent.
- Patient younger than 45 years old, older than 70 years old.

- Off pump patients.
- Patients known hypothyroidism on levothyroxine supplementation.
- Patients known hyperthyroidism on Carbimazole.

Sampling method:

Patients will be randomly allocated by computer generated randomization into two groups A and B:

- **Group A (Study group):** patients receiving oral supplementation of levothyroxine.
- **Group B (Control):** patients receiving Placebo drug.

Anesthetic management:

Full standard preoperative assessment for cardiac surgery will be done for all patients included in the study before planned procedures.

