Premedication will be given according to standard protocol in cardiac anesthesia. Routine monitoring included a five-lead electrocardiogram, pulse oximeter and invasive blood pressure. Anesthesia will be induced with midazolam 0.02mg/kg and fentanyl 2-5 microgram /kg and muscle relaxation were achieved cisatracurium 0.15 mg/kg intravenous. After tracheal intubation, central venous line and TEE inserted, then anesthesia will be maintained throughout the procedure with morphin20 microgram/kg /min, cisatracurium 2mg/kg/min and sevoflurane 2%. Ventilation will be adjusted to maintain end-tidal carbon dioxide in the range of 30-40 mmHg.

On ICU arrival all patients will be subjected to standardized management as per institutional protocols. Patients who show signs of delayed recovery defined as either prolonged ventilation for 48 hours or delayed conscious level recovery for 48 hours despite exclusion of muscle relaxants and/or sedative drugs. Those patients will undergo CT brain, CT chest and neurological examination to exclude structural damage as per institutional protocols. Also, metabolic profile screening including full kidney function, full liver function, electrolyte and thyroid profile (TSH, free T3, free T4) to exclude correctable metabolic abnormalities.

Patients then divided into two groups: group A will receive levothyroxine via Ryle, dose of 25 to 50 ug/ day according to BMI, while group B will receive placebo in form of inert starch tablet.

Daily assessment of conscious level according to Glasgow Coma Scale (GCS) and spontaneous breathing trial by ICU consultant till ICU discharge.

Assessment of thyroid profile (free T3, free T4, TSH) before hospital discharge.

Endpoints of the study:

Primary end point:

1. Improvement of Glasgow coma scale and spontaneous breathing trial before ICU discharge.

Secondary end points:

1. Total ventilation time.
2. Total ICU stay.
3. Total hospital stay.
4. Total amount of inotropic support.
5. Improvement of cardiac function by echocardiography.

Ethical considerations:

The study protocol will receive ethical approval from the Research Ethical Committee, Faculty of Medicine Ain Shams University.

Informed consent will be obtained from each patient before patients' allocation.

Sample Size Calculation

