Using PASS 15.0 (NCSS LLC), detecting an effect size of 0.80 in GCS change ($\alpha = 0.05$, power = 80%) required 25 patients per arm. To ensure adequate power for secondary endpoints and allow for dropouts, we enrolled 35 patients per group (total $n = 70$).

Statistical Analysis

Analyses adhered to the intention-to-treat principle. Continuous variables are reported as mean \pm SD or median (IQR) and compared using Student's t-test or Mann-Whitney U test, as appropriate. Categorical variables are expressed as counts (%) and compared by χ^2 or Fisher's exact test.

- **Primary analysis:** Linear mixed-effects regression modeled GCS trajectories over time, with group, time, and their interaction as fixed effects and patient as a random effect.
- **Time-to-event outcomes:** Kaplan-Meier curves and Cox proportional hazards models yielded hazard ratios (HRs) and 95% confidence intervals (CIs).
- **Mediation:** The Sobel test quantified the proportion of EF preservation attributable to changes in free T3.

- **Sensitivity and subgroup analyses:** Inverse probability weighting assessed robustness; prespecified subgroups included diabetes status and CPB duration > 200 minutes.

All tests were two-tailed with $\alpha < 0.05$. Statistical analyses were performed using R v4.3.1 with the lme4, lavaan, and survminer packages.

4. REFERENCES (Maximum 20 references)

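### The primary mixed model names only patient as a random effect while group-by-time carries the treatment effect; if recovery rates differ between patients, its standard error is too small and false positives rise.

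*Combined protocol and SAP*

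**What the plan says.** Under Statistical Analysis, the primary analysis is described as "Linear mixed-effects regression modeled GCS trajectories over time", "with group, time, and their interaction as fixed effects and patient as a random effect". Patient is the only random term named. The documents mention no random slope, residual correlation structure, robust variance or degrees-of-freedom method. They do not say whether time is linear or categorical, or which coefficient decides the trial. The one robustness method listed is inverse probability weighting, which does not deal with the covariance structure.

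The data feeding the model are described under Anesthetic management: "Daily assessment of conscious level according to Glasgow Coma Scale (GCS) and spontaneous breathing trial by ICU consultant till ICU discharge". No number of days is fixed, so patients will contribute different numbers of scores. Patients qualify by "either prolonged ventilation for 48 hours or delayed conscious level recovery for 48 hours", so two kinds of delayed recovery are mixed.

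The sample size is based on a simpler comparison: "detecting an effect size of 0.80 in GCS change ($\alpha = 0.05$, power = 80%) required 25 patients per arm". Enrolment is then set at 35 per group, 70 in total.

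**The concern.** The primary end point is improvement in GCS, and the model describes trajectories. The treatment effect on recovery is therefore carried by group-by-time, the difference between arms in average slope.

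The precision of that difference depends on how much individual slopes vary. A random intercept absorbs differences in level only. Differences in slope are left in the residual and treated as independent day-to-day noise, so each extra daily score appears to add more independent information about the slope than it does. The standard error becomes too small, and the excess grows with the number of scores.

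Equal recovery rates would be a surprising assumption here. A patient enrolled for prolonged ventilation may have little GCS recovery left to make, while one enrolled for depressed consciousness may have a lot. At stake are the p-value and confidence interval of the trial's only primary test. Because the random structure, time coding and deciding coefficient are all left open, two analysts following the same sentence could reach different conclusions from the same 70 patients.

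**Working it through.** **The plan's own figure.** For an effect size of 0.80, two-sided 5% alpha and 80% power, the normal approximation gives 2 × (1.960 + 0.842)² / 0.80² = 24.5, so 25 per arm. This matches the plan, which refers to a z test. It comes from a two-sample comparison, so it neither tests nor depends on the mixed model's covariance.

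**Inputs from the documents.** 35 per arm (N = 70), daily GCS, group-by-time, patient as the only random term, two-sided 5%.

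**Assumed, because the documents give no values.** Linear time; m = 3, 5 or 8 daily scores; residual SD (se) 1 or 2 points; SD of patient slopes (sb) 0 to 0.5 points per day.

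**Formulas**, with S the sum of squared centred days (2, 10 and 42 for m = 3, 5 and 8):

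- True variance of group-by-day = (2/35)(sb² + se²/S)
- Variance reported by the random-intercept model = (2/35)(se² + sb²·S·(N−2)/(N(m−1)−2))/S
- Actual alpha = 2 × (1 − Φ(1.96 × √(reported/true)))

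**Worked case: m = 5, se = 1, sb = 0.3.** True: (2/35)(0.09 + 0.10) = 0.01086, SE 0.104. Reported: (2/35)(1 + 0.09 × 10 × 68/278)/10 = (2/35)(0.1220) = 0.00697, SE 0.083. The ratio of standard errors is 0.801, and 1.96 × 0.801 = 1.571, which gives an actual alpha of 0.116.

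**Actual alpha, residual SD 1:**

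| Slope SD | 3 scores | 5 scores | 8 scores |
|---|---|---|---|
| 0 | 0.050 | 0.050 | 0.050 |
| 0.1 | 0.051 | 0.059 | 0.091 |
| 0.2 | 0.055 | 0.083 | 0.184 |
| 0.3 | 0.060 | 0.116 | 0.268 |
| 0.5 | 0.074 | 0.184 | 0.364 |

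For slope SD 0.1 to 0.5, correct intervals would be 1.04 to 1.47 times as wide with 5 scores and 1.16 to 2.16 times with 8. With residual SD 2, alpha runs 0.050-0.057, 0.052-0.099 and 0.060-0.229 for 3, 5 and 8 scores.

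**Check by simulation** (REML random-intercept fits, 2,000 null trials per scenario, slope SD 0.1/0.2/0.3/0.5). Balanced data gave 0.060/0.092/0.108/0.184 with 5 scores and 0.093/0.166/0.261/0.359 with 8, in line with the formula.

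**Bounded scores and early stopping.** Scores were rounded, limited to 3-15 and stopped at the first value of 14 or more (assumed starting mean 9, SD 2, mean slope 0.5 per day). Results were 0.050/0.047/0.074/0.066 with 3 scores, 0.054/0.084/0.114/0.172 with 5 and 0.080/0.171/0.235/0.316 with 8.

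**Unequal stays.** With stays of 3 to 11 days and slope SD 0.3, a smaller simulation gave 0.377 (377 fits; mean reported SE 0.048, actual SD 0.108), and 0.351 with scores limited to 3-15 (547 fits).

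**Categorical days with a joint group-by-day test** (20,000 trials, same slope SDs). Results were 0.051/0.050/0.051/0.051 with 3 scores, 0.051/0.050/0.057/0.067 with 5 and 0.054/0.064/0.081/0.115 with 8.

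**Does the remedy work?** Comparing patient-level slopes between arms on balanced data gave 0.045-0.056. A random-slope analysis that reverts to the intercept model when the slope variance is estimated at zero gave 0.045-0.057. Leverage-corrected patient-clustered errors on the random-intercept fit (t, 68 df) gave 0.039-0.060 over 30 scenarios. REML random-intercept-and-slope fits gave 0.030-0.074, but from only 262 to 547 fits per scenario.

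**The case against.** The strongest reply is that the defect is read into a short phrase. The text does not say intercept only, and lme4, which the plan names, can fit a random slope. Material inflation needs an intercept-only model, slopes that vary and enough daily scores, and it is large only with linear time. With 3 scores, or with categorical days and up to 5 scores, error stays at about 7% or less. With only two time points the formula gives exactly 5%. The 36% corner implies a last-day GCS SD of √(2² + 49 × 0.5² + 1²) = 4.15 with an intercept SD of 2. That is wider than a uniform spread over 3-15 (SD 3.74), so it should not be taken as typical.

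Much of this stands as a limit on size. The top of the range is an extreme, although the bounded simulation still reaches 32%. The rest does not remove the problem. A lone patient effect is ordinarily read as a random intercept, and nothing elsewhere supplies a slope or a robust variance. A two-point model does not fit daily scoring or a trajectory analysis.

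Two practical points are fair. With few scores the slope variance will often be estimated at zero (about 47% of trials with 3 scores and slope SD 0.1, residual SD 1). Such a fit is not a convergence failure, so the plan needs a rule for it. The section is also written in the past tense; if the analysis has already been run, a changed model would have to be disclosed as such.

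**Conclusion.** The concern holds. Followed as written, the primary model understates the uncertainty of group-by-time whenever recovery rates differ between patients, and no safeguard appears elsewhere in the documents. The direction and mechanism are certain under that condition. The size is not, because it rests on assumed slope and residual SDs and on an unstated number of daily scores. Under linear time it runs from negligible with 3 scores to several times the nominal 5% with 8, with larger error possible when stays are long or unequal. Under a joint categorical-day test it is much smaller. If slopes do not vary, there is no inflation. Confidence in the exact size is moderate; the required sample of 25 per arm is not affected.

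**What to change.** State in the Primary analysis item:

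- Time is coded as linear day, and group-by-day is the primary coefficient.
- GCS is modelled on group, day and group-by-day, with a random intercept and a random slope for day per patient (lme4: `1 + day | patient`), and Satterthwaite or Kenward-Roger degrees of freedom.
- If the model does not converge, the same fixed effects are kept and patient-clustered, small-sample-corrected robust standard errors are used.
- If the slope variance is estimated at zero, a rule fixed in advance applies; reverting to the intercept model kept error near 5% in simulation.

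If categorical days are preferred, the plan should name the contrast and its covariance structure, since inflation there is smaller but not zero.

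The cost is one or two sentences of SAP text plus the zero-variance rule, with no new data. Intervals for the primary coefficient will be wider, and convergence may be difficult with 70 patients. An R package beyond the three in the plan ("Statistical analyses were performed using R v4.3.1 with the lme4, lavaan, and survminer packages") is needed for the degrees of freedom or robust errors. If results already exist, both analyses should be reported and the change labelled as made afterwards. This change does not deal with follow-up ending at ICU discharge, which is a separate issue.

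### The primary GCS model makes no baseline use of the allocation-day score, so it gives up precision and leaves the estimate exposed to chance imbalance; the model is otherwise valid

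*Combined protocol and SAP*

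**What the plan says.** All references are to the combined protocol and SAP.

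- **Statistical Analysis, primary analysis:** "Linear mixed-effects regression modeled GCS trajectories over time", "with group, time, and their interaction as fixed effects and patient as a random effect". No baseline GCS covariate and no common-baseline constraint is stated. Inverse probability weighting appears only as a sensitivity analysis, without a list of variables.
- **Sample Size Calculation:** the basis is "detecting an effect size of 0.80 in GCS change", giving 25 per arm. The section continues: "To ensure adequate power for secondary endpoints and allow for dropouts, we enrolled 35 patients per group".
- **Section 3, Methodology:** allocation is computer-randomised. Patients are divided into arms and treated only after the 48-hour delayed-recovery work-up. GCS is then assessed daily until ICU discharge. The primary end point is improvement in GCS and in the spontaneous breathing trial.

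The text does not say whether the allocation-day GCS is one of the modelled responses, whether time is categorical or continuous, or which coefficient is the primary test. A pre-dose GCS is implied by the use of change, but no section schedules it explicitly.

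**The concern.** Because patients are randomised before the first dose, the expected allocation-day GCS is the same in both arms. That knowledge is free, and the stated model does not use it. There are two readings.

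1. **The allocation-day score is a response row.** A group main effect beside group-by-time gives each arm its own starting mean, and the interaction measures departure from those two means. This works like a comparison of change scores: any chance gap at the start is subtracted in full, although only part of it would persist.
2. **It is not a response row.** The arms are then compared on post-allocation GCS with no adjustment, and the part of a chance starting gap that does persist stays in the result.

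The two readings err in opposite directions, but both leave the estimate correlated with starting imbalance and both have a larger variance than the same data allow. With 70 patients, a visible starting difference would also make the primary result harder to interpret.

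**Working it through.** **Inputs from the documents.** Standardised effect 0.80 on GCS change; "setting power at 80% and alpha error at 0.05"; "All tests were two-tailed"; 25 per arm planned and 35 per arm enrolled. **Assumed, because the documents give neither correlation nor SDs:** baseline to follow-up correlation ρ = 0.3 / 0.5 / 0.7 and, except in step 5, equal SDs at baseline and follow-up.

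**1. The plan's own figure.** n = 2 × (1.960 + 0.842)² / 0.80² = 24.53, rounded up to 25 per arm. This reproduces the stated number (a t-test would need 26). At 35 per arm, power for 0.80 is 0.92 by the normal approximation and 0.91 by the t-test, before any dropout.

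**2. Reading 1, change from allocation to one given day.** In units of the GCS variance, a change score has variance 2(1−ρ) and a baseline-adjusted score has 1−ρ². The ratio is (1−ρ²) / [2(1−ρ)] = (1+ρ)/2.

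| ρ | Variance ratio | Equivalent extra patients (1/ratio − 1) | Effect detectable at 35 per arm, 80% power |
|---|---|---|---|
| unadjusted | 1 | – | 0.68 SD of change |
| 0.3 | 0.65 | 54% | 0.55 |
| 0.5 | 0.75 | 33% | 0.59 |
| 0.7 | 0.85 | 18% | 0.63 |

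The last column is 0.68 × √ratio. A generalised least squares calculation with categorical time gives the same ratios. A simulation of 20,000 trials per ρ gives 0.66 / 0.76 / 0.86, slightly higher because the regression slope is estimated.

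**3. Reading 2, unadjusted final-day difference.** The ratio is 1−ρ² = 0.91 / 0.75 / 0.51. Here the gain grows with correlation, whereas in step 2 it shrinks.

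**4. Linear slope, days 0-7.** Generalised least squares with a random intercept (ρ is then the intraclass correlation) compares the variance of the group-by-time coefficient with and without the group main effect: 0.65 / 0.79 / 0.89. With random slopes (slope variance 2% of intercept variance) it is 0.75 / 0.89 / 0.96.

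**5. Unequal SDs.** Let k be the follow-up SD divided by the baseline SD. The ratio in step 2 becomes k²(1−ρ²) / (1 + k² − 2ρk). At ρ = 0.5:
- k = 0.5: 0.1875 / 0.75 = 0.25
- k = 1: 0.75 / 1 = 0.75
- k = 2: 3 / 3 = 1.00, so no gain

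**6. Dependence on chance imbalance.** The standard error of the allocation-day difference at 35 per arm is √(2/35) = 0.24 SD of GCS. An imbalance of one standard error in favour of an arm shifts the result, in SD of GCS, by:
- change contrast, −(1−ρ) × 0.239: −0.17 / −0.12 / −0.07
- unadjusted final-day contrast, ρ × 0.239: +0.07 / +0.12 / +0.17

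In the simulation the change contrast correlates with the imbalance at −0.59 / −0.50 / −0.39. After adjustment the correlation is about 0. The mean error is about 0 for both estimators.

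**The case against.** The strongest reply is that group, time and their interaction is a conventional and valid model. That stands. Over repeated trials it is unbiased, and its standard error already reflects chance imbalance. A reader might infer that the primary result is biased or that false positives are inflated; neither the documents nor the simulation support that. The cost is variance, and dependence on the imbalance in the one trial at hand.

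A reader might also infer that the trial is underpowered for GCS. It is not, on its own assumptions: the unadjusted detectable effect of 0.68 is already below the planned 0.80.

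It is tempting, too, to state as fact that the model fits a separate allocation-day mean in each arm. The documents do not go that far, since they never say that the allocation-day score is a modelled response. The point survives because neither reading uses the baseline, but its size and direction differ between them.

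Finally, the gain may be small. GCS is bounded and one entry route selects on delayed consciousness, so equal SDs are not assured, and step 5 shows the gain can vanish. It also shrinks with random slopes, or with high correlation under the change contrast (standard error only 2.5% lower at ρ = 0.9). All of this stands and limits the claim to an improvement of unknown size.

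**Conclusion.** The point holds as a matter of efficiency and robustness. The primary GCS analysis makes no baseline use of a score that the sample-size basis implies will exist, so it forgoes precision and leaves the estimate tied to chance starting differences. Under equal SDs and correlations of 0.3 to 0.7, the variance after adjustment would be roughly 0.5 to 0.95 of its present value, depending on the contrast tested and the random-effects structure. With unequal SDs the change-contrast gain could be larger or nil. The correlation and the SDs are assumptions throughout. The planned 25 per arm and the enrolled 35 per arm are not called into question.

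**What to change.** Choose one of two forms and state it in the Statistical Analysis section:

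- **Covariate form.** Model post-allocation daily GCS, with the GCS recorded at allocation before the first dose as a covariate, keeping group, time and group-by-time. Name the primary contrast, for example the arm difference at a stated day or averaged over stated days. The naming matters: under a random intercept, a baseline covariate entered only as a main effect leaves a slope difference across post-allocation days essentially unchanged.
- **Common-mean form.** Include the pre-dose score as time zero with one mean for both arms (time and group-by-time, no group main effect), and treat time as categorical or otherwise flexible. With linear time, dropping the group main effect would force the arms to diverge in a straight line from zero and would misfit an early plateau.

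Keep the stated model as a sensitivity analysis.

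The cost is a few sentences and no new patients. The plan should confirm that a GCS is recorded at allocation before the first dose, because this is implied but not scheduled. The Sample Size Calculation and Statistical Analysis sections are written in the past tense, so if outcome data have already been seen, the changed analysis should be labelled post hoc.

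### CPB duration, diabetes and surgical urgency are fixed before allocation, but no secondary analysis names them as covariates: a loss of efficiency, not a bias

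*Combined protocol and SAP*

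**What the plan says.** The Statistical Analysis section assigns two-sample tests to continuous and categorical variables. For time-to-event outcomes it says that "Kaplan-Meier curves and Cox proportional hazards models yielded hazard ratios (HRs) and 95% confidence intervals (CIs", without naming a covariate or saying which endpoints are analysed this way. The secondary endpoints are total ventilation time, ICU stay, hospital stay, inotropic support and echocardiographic function.

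The three factors appear elsewhere. Under sensitivity and subgroup analyses, "prespecified subgroups included diabetes status and CPB duration > 200 minutes". Urgency appears only in the inclusion criteria: "Elective, urgent and emergency open heart surgeries". Randomization is not described as stratified. Inverse probability weighting is listed as a robustness check, with no variables or endpoints given.

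The Methodology section places allocation in the ICU, after 48 hours of prolonged ventilation or delayed consciousness and after the imaging and metabolic work-up. Off-pump patients are excluded.

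**The concern.** In many perioperative trials CPB time is a post-randomization variable and cannot be used for adjustment. Here surgery is over before anyone is allocated, so CPB duration, diabetes and urgency cannot be affected by treatment. The planned subgroups already require the first two, the third is part of the entry description, and every participant has a CPB duration.

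The Sample Size Calculation section gives power for secondary endpoints as one reason for going from 25 to 35 per arm. If the three factors predict recovery, unadjusted comparisons give up part of that gain. Silence on the Cox covariates also leaves room to choose them after the results are seen.

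**Working it through.** **The plan's own figure.** Inputs: "setting power at 80% and alpha error at 0.05" (Sample Size); "All tests were two-tailed" (Statistical Analysis); "detecting an effect size of 0.80 in GCS change" (Sample Size Calculation); equal arms, "25 patients per group total 50 patients" (Sample Size). Normal approximation: n per arm = 2 × (1.960 + 0.842)² / 0.80² = 15.70 / 0.64 = 24.5, so 25. This reproduces "required 25 patients per arm". A noncentral t calculation gives 79.1% power at 25 and 80.7% at 26, which is close enough.

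**What 35 per arm can detect without adjustment**, if all 70 contribute:
- Continuous endpoint: 2.80 × √(2/35) = 0.67 SD at 80% power.
- Cox model, all 70 with an event: exp(2.80 / √(70/4)) = exp(0.67) = 1.95 at 80% power. At a hazard ratio of 1.75, power is 65%.

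**Continuous endpoints with adjustment.** If the covariates explain a share R² of the variance, the detectable difference is multiplied by √(1 − R²) and the equivalent unadjusted sample size is 35 / (1 − R²). R² is assumed.

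| R² | Detectable difference | Equivalent n per arm | Power at 0.67 SD |
|---|---|---|---|
| 0 | 0.67 SD | 35 | 80% |
| 10% | 0.67 × 0.949 = 0.64 SD | 39 | 84% |
| 20% | 0.67 × 0.894 = 0.60 SD | 44 | 88% |
| 30% | 0.67 × 0.837 = 0.56 SD | 50 | 92% |

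**Cox models with adjustment.** Simulated trials: 35 per arm, exponential times, conditional hazard ratio 2.0, 90% with an event, a standard-normal prognostic score of assumed strength. The first three rows use 3,000 trials and fit three covariate terms; the last three use 1,500 trials and fit the score itself.

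| Log-HR per SD | Power unadjusted | Power adjusted | Gain (points) | Mean unadjusted HR |
|---|---|---|---|---|
| 0 | 76.8% | 76.5% | −0.3 | not recorded |
| 0.1 | 76.0% | 76.0% | 0 | not recorded |
| 0.2 | 74.2% | 76.6% | 2.4 | not recorded |
| 0.3 | 72% | 77% | 5 | 1.93 |
| 0.5 | 64% | 76% | 12 | 1.83 |
| 0.7 | 53% | 74% | 21 | 1.71 |

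A repeat of the last three rows with 3,000 trials gave about 72%, 66% and 54% unadjusted against 77%, 78% and 75% adjusted.

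**A second parameterisation.** Three binary covariates (assumed prevalences 35%, 35% and 30%), conditional hazard ratio 1.95, all 70 with events. With each covariate's hazard ratio at 1.25, 1.5 or 2.0, the large-sample unadjusted hazard ratio is about 1.90, 1.83 or 1.71. Power is 74% against 76%, 70% against 76%, and 58% against 76%. The pattern is the same.

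**Type I error.** In the normal-score setting, rejection under the null was 4.8-5.6% unadjusted and 5.7-6.4% with three terms fitted. In the binary-covariate setting it was 3.5-6.3% and 4.6-6.5% (1,500 trials each; standard error √(0.05 × 0.95 / 1,500) = 0.6 points). With three terms the mean adjusted hazard ratio was about 2.05-2.09 against a true 2.0.

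**The case against.** The strongest reply is that nothing here is invalid. A reader might infer that the unadjusted hazard ratios are biased, or understate a real effect. The documents do not support that. Under randomization the unadjusted hazard ratio estimates a marginal effect and the adjusted one a conditional effect; they differ because the hazard ratio is non-collapsible. The t-test's mean difference is not attenuated at all. Nor does chance imbalance make the unadjusted interval wrong, since the interval already allows for it. All of this stands.

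The loss may also be negligible. The documents give no prognostic strength for any of the three factors. Choosing two as subgroups shows interest in effect modification, not evidence that they predict outcome. Everyone entering has already had 48 hours of delayed recovery, which could weaken such predictors. The top of the range is strong: top- and bottom-decile averages of a normal score lie about 3.51 SD apart, so 0.7 per SD implies exp(0.7 × 3.51) ≈ 12-fold between them. This stands too, and is why the range has to start at zero.

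The remaining replies carry less weight. Inverse probability weighting could use these variables, but it is only a sensitivity analysis and names none. Subgroups do not adjust the main comparison, and a cut at 200 minutes discards the information in CPB duration on each side of it. The plan is silent on Cox covariates and does not rule them out, so it cannot be read as committed to unadjusted Cox models; the t-test and Mann-Whitney comparisons are plainly unadjusted.

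**Conclusion.** The point holds as one of efficiency and prespecification for the secondary endpoints. Three genuine baseline variables are available and no stated secondary comparison adjusts for them. At 35 per arm and a hazard ratio near 2, the Cox power forgone runs from nothing or about 2 points (log-HR 0-0.2 per SD), through about 5 (0.3), to about 20 (0.7). For continuous endpoints the detectable difference could fall from 0.67 SD to 0.64-0.56 SD if the covariates explain 10-30% of variance.

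These sizes rest on assumed prognostic strength, proportional hazards with exponential times, 90-100% of patients having an event, and no loss from the 70. The direction depends only on the factors being prognostic. The validity of the planned tests is not in question.

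**What to change.** In the Statistical Analysis section:

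- Prespecify log CPB duration (continuous), diabetes (yes/no) and urgency (elective versus urgent/emergency) as covariates in the Cox models, and state that the adjusted hazard ratio is conditional.
- For each duration endpoint, say whether the adjusted Cox model or an adjusted linear regression is the lead analysis. If it is the regression, say how deaths are handled.
- For inotrope amount, use an adjusted method that tolerates zeros, such as rank-based ANCOVA or a proportional-odds model. A plain log transform fails for any patient who receives none, and nothing in the entry criteria requires inotrope use.
- Show the unadjusted results alongside.

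The cost is wording, plus three model terms: with 70 events, treatment and three covariates leave 70 / 4 = 17.5 events per parameter. There is a small downside: slight small-sample inflation of the adjusted hazard ratio and of type I error (about 6% in simulation), and no gain if the factors are not prognostic. The section is written in the past tense, so if outcomes by group have already been seen, the adjusted analyses should be labelled post hoc.

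### The mediation sentence asks the Sobel test for a proportion it cannot supply, and states no path model, total effect or interval

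*Combined protocol and SAP*

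**What the plan says.** The whole mediation plan is one bullet under Statistical Analysis: "The Sobel test quantified the proportion of EF preservation attributable to changes in free T3".

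Three other places bear on it:

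- **Mediator.** Free T3 is part of the metabolic screen before allocation. The only follow-up value is in the Methodology: "Assessment of thyroid profile (free T3, free T4, TSH) before hospital discharge".
- **Outcome.** The fifth secondary end point is "Improvement of cardiac function by echocardiography". No time point is given, and EF is named only in the mediation bullet.
- **Software.** "Statistical analyses were performed using R v4.3.1 with the lme4, lavaan, and survminer packages". No path model is described.

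The Sample Size Calculation section gives 35 patients per group, 70 in total, and bases this on GCS change. Mediation has no power statement.

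**The concern.** The sentence names a test and attaches to it a result that the test does not produce. A Sobel test returns a z statistic and a p-value for the product of two regression coefficients. A proportion mediated is a ratio of that product to the total effect. It needs its own estimate and its own interval, and the plan gives neither.

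This is the plan's only mechanistic analysis. Followed literally, it could lead to a reported share of the EF effect due to free T3 with no defined estimand and no measure of uncertainty. In a trial of 70 patients such a ratio can look precise while being almost uninformative. The normal approximation behind the Sobel test also fits a product of coefficients poorly at this size, so a real indirect effect would be missed more often than necessary.

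**Working it through.** **Inputs from the documents.** 35 per arm; two-sided 5% level; Sobel test; lavaan listed. **Not in the documents:** path sizes, and SDs for EF or free T3. All path values below are assumptions, with residual SD 1 and no baseline adjustment.

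**1. The plan's own figure.** "detecting an effect size of 0.80 in GCS change ($\alpha = 0.05$, power = 80%) required 25 patients per arm". With a two-sided z test, n = 2(1.960 + 0.842)² / 0.80² = 15.70 / 0.64 = 24.5, so 25 per arm (power 80.7%). The figure reproduces and is not in dispute, but it concerns GCS, not mediation.

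**2. Does the Sobel statistic determine a proportion?** Let a be the effect of allocation on free T3, b the effect of free T3 on EF given allocation, and c′ the direct effect.

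- Sobel z = ab / √(a²·SE_b² + b²·SE_a²)
- Proportion mediated = ab / (ab + c′)

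Take a = 0.8 (SE 0.24) and b = 0.3 (SE 0.12). Then ab = 0.24 and z = 0.24 / √(0.64 × 0.0144 + 0.09 × 0.0576) = 0.24 / √0.0144 = 2.0, whatever c′ is.

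| c′ | Sobel z | Proportion mediated |
|---|---|---|
| 0 | 2.0 | 100% |
| 0.24 | 2.0 | 0.24/0.48 = 50% |
| 0.72 | 2.0 | 0.24/0.96 = 25% |
| 2.16 | 2.0 | 0.24/2.40 = 10% |

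One test result is compatible with any of these shares.

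**3. Power for the indirect effect at n = 70** (2,000 simulated trials, 1,000 resamples each). Power does not depend on c′, because the estimates of a and b do not.

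| a | b | Sobel | Percentile bootstrap | Gap (points) |
|---|---|---|---|---|
| 0.5 | 0.3 | 16% | 34% | 18 |
| 0.6 | 0.4 | 44% | 63% | 19 |
| 0.8 | 0.3 | 44% | 61% | 17 |
| 1.2 | 0.4 | 85% | 89% | 4 |
| 1.5 | 0.4 | 89% | 90% | 1 |

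A separate run of five scenarios gave 20%/38%, 45%/64%, 43%/61%, 85%/88% and 87%/89%: gaps of 18, 19, 18, 3 and 2 points. Joint-significance and Monte Carlo intervals (4,000 trials) point the same way. At a = 0.8, b = 0.5 the Sobel test had 80% against 88% and 87%; at a = 1.2, b = 0.3 it had 60% against 66% and 67%.

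**4. Error rate.** The informative null is one where treatment moves T3 but T3 does not affect EF (b = 0). For a from 0.8 to 1.5 the Sobel test rejected about 2% to 4%. The bootstrap rejected about 6% to 8% in one run; others gave 4.4% and 5.8% at a = 0.8, and 6.4% at a = 1.2 and at a = 1.5.

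**5. Stability of the ratio.**

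| a, b, c′ | True proportion | Central 95% of estimates | Outside 0–1 |
|---|---|---|---|
| 0.5, 0.3, 0.35 | 0.15/0.50 = 0.30 | −0.20 to 1.56 | 10% |
| 0.6, 0.4, 0.2 | 0.24/0.44 = 0.55 | −1.27 to 3.11 | 20% |
| 0.8, 0.3, 0.3 | 0.24/0.54 = 0.44 | 0.01 to 2.14 | 13% |
| 0.8, 0.3, 0.56 | 0.24/0.80 = 0.30 | 0.04 to 0.86 | 2% |

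The separate run in step 3 gave 10% to 23% outside 0 to 1. Three further settings (a = 0.8, b = 0.4; a = 0.8, b = 0.5; a = 1.2, b = 0.3; each with c′ = 0.4) gave 6% to 8%. The extreme percentiles move between runs, as expected for a ratio.

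**The case against.** The best defence is that lavaan is a path-model package. A sympathetic reader would take the proportion to come from a fitted path model and the Sobel test to supply only its significance. Part of this stands: a reader might infer that the trial could not produce a proportion at all, and that is too strong, since the listed software can estimate one. But the plan describes no such model, ratio or interval, and the sentence as written gives the task to the test.

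Second, the power loss depends on inputs that nobody can take from these documents. This stands. A reader might infer a loss of nearly 20 points as a property of this trial. That holds only for modest treatment-to-T3 paths; if free T3 moves by 1.2 SD or more, the loss is small.

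Third, a reader might assume that the bootstrap's gain costs nothing in error rate. It does not hold the level exactly: when T3 moves but has no effect on EF, it can reject slightly above 5%.

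Fourth, a reader might infer that free T3 is drawn after the echocardiogram, and wish to restrict the analysis to patients sampled in the right order. The documents give no echocardiogram time, so the order is unknown, not wrong. Such a restriction would also select patients on an event after randomisation.

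Finally, mediation is not a listed end point. This stands, and it limits how much the point matters.

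**Conclusion.** The point holds in a limited form. That the Sobel test cannot quantify a proportion mediated follows from its formula and needs no assumption. That the plan states no path model, total effect or interval is plain from the text.

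The numerical claims are conditional on linear models, unit residual SDs, complete data on 35 per arm and assumed path sizes. They show a direction and a range, not a forecast for this trial. The usable number may be below 70, because a patient who dies before discharge may have no follow-up free T3.

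Nothing here touches the primary GCS analysis or any comparison between the arms. It should be corrected as a defect in a supporting analysis.

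**What to change.** Replace the mediation bullet with:

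> As an exploratory analysis, the indirect, direct and total effects of allocation on EF, with free T3 as mediator, are estimated in lavaan, adjusted for baseline free T3 and for baseline EF where recorded, each with a percentile bootstrap 95% CI (5,000 resamples). Any proportion mediated is reported with its bootstrap CI and is not interpreted when the CI for the total effect includes zero.

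Also state the times of the follow-up free T3 sample and of the echocardiogram. Report their order, and the number of patients with both, as a limitation. Do not exclude patients on that order.

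The cost is a few sentences of plan text and a few lines of code in a package already listed. The downsides are that the proportion may turn out not to be interpretable, that the bootstrap may run slightly above its nominal level as shown, and that unmeasured confounding between free T3 and EF remains whichever interval is used.
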